### **Aim 1 - Qualitative Review:**

The audiotaped focus group and individual interview is the primary data that will be collected from participants. The only other information collected will be on a locator form. The locator form records the participant's home and work telephone, address, and email. This information will be used to schedule and prompt participants to join their focus group and to contact them for any follow-up questions after the focus group, if needed for clarification.

As indicated above, an inductive approach will be used to identify themes and subthemes in the audiotaped recordings. A codebook will be used in NVivo software to assess transcripts. A content analysis will be performed and used to identify refinement themes. The product team will confer with team experts where appropriate to propose product solutions to the refinements.

### **Aim 2- Training Intervention:**

#### ***Data collected directly from participants:***

Surveys for baseline, post tutorial (i.e., 2-weeks post baseline), and 12-weeks post baseline assessments will be self-administered using Alchemer software since participants may be located anywhere across the country. The baseline survey consists of socio-demographic questions, such as gender, age, race/ethnicity; other standardized socio-demographic measures adapted from the GPRA instrument; a CRAFT Knowledge Test; and a Training Expectations Form.

Each assessment point also will include an audiotaped mock client session conducted via web conferencing with a standardized patient portrayed by a professional actor. Using a standardized patient will provide a consistent context for measuring counselors' CRAFT skill level at each time-point. The mock session will present the counselor with an opportunity to roleplay CRAFT procedure: teaching the CSO to invite the IP to enter treatment (the same procedure is required for the follow-up assessments). We chose to assess this procedure because a component analysis study showed it positively impacted treatment entry rates and it requires CRAFT skill accumulation (i.e., it incorporates and builds upon skills trained in communication and positive reinforcement). Audio tapes will be coded using the CRAFT Therapist Coding Manual used by [name] to certify counselors.

At the post-tutorial and 12-week follow-up assessments additional surveys will be added regarding satisfaction with the training program, perceptions of usefulness and usability, implementation potential, and program value. Finally, at the 12-week follow-up only, participants will be asked to report the number of CSOs they have worked with over the past 10 weeks, how many of them they implemented CRAFT with, and how many of those CSOs had a loved one who entered new treatment. The measures, their purposes, related hypotheses, and assessment points are provided in the **Measures Table** below.

Table 3. Measures

Purpose	Hypothesis	Measure	Assessment points 
Counselor Knowledge and Skill	i. TMC>TM>T	CRAFT Therapist coding Manual***	Pre-Tutorial, Post-Tutorial, 12 weeks
	ii TMC>TM>T	CRAFT Knowledge Test**	Pre-Tutorial, Post-Tutorial, 12 weeks
Acceptability and Feasibility	iii	Training Expectations Form x	Pre-Tutorial
	iii	Training Satisfaction Survey x	Post-Tutorial, 12 weeks
	iii	Usefulness and Usability Assessment x	Post-Tutorial, 12 weeks
	iv	Implementation Potential Scale x	Post-Tutorial, 12 weeks
	v	Price Sensitivity Survey x	Post-Tutorial, 12 weeks
	vi	Treatment Entry and Retention	12 weeks

 Phase 2 will use the same assessment points plus a 6 mo follow up. Note: Training Expectations Form is a baseline version of the Training Satisfaction Survey.

Revised measures have been adapted specifically for professional participants as appropriate.

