  - 2.3. Participants in all conditions will perceive increased implementation potential over time (pre-tutorial, post-tutorial, 12 week follow up), but at 12 weeks implementation potential will be lower for TMC compared to TM and T.

*Rationale:* In a CBT (Cognitive Behavioral Therapy) web-based training study implementation potential of three training programs increased over time, but a condition involving expert supervision was seen as more difficult to implement.
  - 2.4. Participants assigned to the TMC condition will assign the highest monetary value to the tutorial, digital training and certification components, followed by TM and then T participants, in their 12-week follow-up surveys.

*Rationale:* The pilot study of our CRAFT Family product showed participants assigned to the CRAFT private coaching condition valued all components of the program substantially higher than those who received less coaching in the group condition, or digital only (no coaching) condition.
  - 2.5. Participants assigned to the TMC condition will report that more IPs have entered treatment compared to TM and T at 12-weeks (after study start) follow-up surveys.

*Rationale:* This hypothesis is based on the results from previous trials examining counselor fidelity and studies showing that CBT fidelity enhances treatment outcome. *We consider this hypothesis exploratory because the 6 month timeline will not be sufficient to adequately test for differences in treatment entry, as there would not be much time after all counselors completed training for them to complete CRAFT with CSOs.*

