#### **Aim 2 - Training Intervention:**

Because we believe that counselors may have heightened willingness to participate in the study if the tutorial is supported by their place of employment, we will recruit through free tutorials offered to OUD treatment clinics targeting those focused on family services. Our recruitment efforts will be limited to the United States and will begin in the first project quarter following IRB approval and grant award. Recruitment will continue through the first quarter of the project or until we recruit up to 45 eligible participants, whichever comes first. We will track and document which recruitment strategies yield the best engagement. Please see examples of images and messaging we will use for different methods of recruitment. We plan to implement the following recruitment methods:

1. Recruitment channels for Training Intervention
  - a. WTV Promotions (e.g., website callouts, emails, social media posts and 1:1 message) to existing and future WTV members.
  - b. Engagement of the WTV membership group to suggest this opportunity to their network and make a referral if they know anyone who fits the participant description.
  - c. Outreach to existing partners who provide services to patients with OUD.
    - i. Wholeview Wellness
    - ii. Center for Motivation and Change
    - iii. JoinGroups.Com (medication-assisted treatment (MAT) for opioid addiction)
  - d. Provide free tutorials offered to OUD treatment clinics targeting those focused on family services and programs
    - i. Counselor listservs (such as: State chapters of Professional Liaison's Association, e.g. NYPLA, American Counseling Association, National Board of Certified Counselors)
    - ii. Listings of treatment programs will be obtained from the SAMHSA website and web-based directories associated with state related SUD offices.
  - e. Develop recruitment strategies to increase diversification of study participants
    - i. Promote research study on the following professional counseling member websites:
      - Association of Black Psychologists (ABPsi)
      - National Association of Black Social Workers (NABSW)
    - ii. Develop new partnerships with providers who serve more diverse populations, including communities of color and lower SES
  - f. Targeted digital and local advertising efforts.
    - i. NADAAC
    - ii. Facebook
    - iii. Instagram
    - iv. Google

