  - a. **Discomfort associated with being audiotaped during the focus group, individual interviews, or mock or actual sessions.** We will help participants to understand that feeling uncomfortable when being audiotaped is usually transitory. For participants submitting audiotapes of mock or actual client sessions, we will clarify that our goal is to evaluate the training programs, not their abilities per se. If participants experience significant distress such that it makes participation uncomfortable for them, they will be reminded that they can leave the study at any time.
  - b. **Discomfort associated with the training intervention (Aim 2 only)** - The level of distress associated with training interventions is expected to be similar to that which they would experience during any training program and is not a function of the research participation per se. Nonetheless, participants will be informed about this possible risk before consenting and will be told that they can withdraw from the study at any time without penalty. If participants in the TMC condition are experiencing difficulty, discomfort, or distress associated with locating CSOs for actual client sessions, we will help facilitate a client match for them from our We The Village community of family members with a loved one struggling with OUD. If they are experiencing discomfort due to concerns about protecting client confidentiality for those clients participating in videotaped sessions, we will discuss with them steps to ensure client consent and to protect client confidentiality.
3. **Disappointment associated with the training intervention (Aim 2 only)** – It is possible that counselors will be disappointed with the training condition to which they are randomly assigned. Counselors assigned to the T and TM conditions may be disappointed that they did not receive a more intensive training opportunity that would allow them to become certified as CRAFT counselors. Should these individuals wish to pursue CRAFT certification through We The Village after their research participation has ended they will not be charged for the components they have already received and can complete certification at a reduced cost. Counselors who are randomly assigned to the TMC training program may be disappointed that they did not receive a less intensive training program. These individuals, like all study participants, are free to withdraw from the study at any time.

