Rationale: Direct observation measuring content of CRAFT delivered in treatment sessions is our primary outcome as this provides the best assessment of counselor adherence and skill and is consistent with previous studies.^{7,10,41} Our hypothesis that TMC will produce greater use of CRAFT than T (or TM) is based on the results from previous trials comparing a workshop only to workshops plus feedback and coaching.^{7,10,41}
2. Secondary Hypotheses
 - 2.1. Participants assigned to the TMC condition will demonstrate the highest CRAFT knowledge followed by TM and then T, in their 12-week knowledge test.
Rationale: Results from previous controlled trials have shown no differences in counselor knowledge pre- to post-workshop, but increases have been seen when fact sheets and supervision are added after the workshop.^{39,57-58}
 - 2.2. Participants in all conditions will perceive increased implementation potential over time (pre-tutorial, post-tutorial, 12 week follow up), but at 12 weeks implementation potential will be lower for TMC compared to TM and T.
Rationale: In a CBT (Cognitive Behavioral Therapy) web-based training study implementation potential of three training programs increased over time, but a condition involving expert supervision was seen as more difficult to implement.³⁹

2.3. Participants assigned to the TMC condition will report that more IPs have entered treatment compared to TM and T at 12-weeks (after study start) follow-up surveys. *Rationale:* This hypothesis is based on the results from previous trials examining counselor fidelity^{7,10,41} and studies showing that CBT fidelity enhances treatment outcome.⁵⁹⁻⁶⁰ *We consider this hypothesis exploratory because the 6 month timeline will not be sufficient to adequately test for differences in treatment entry, as there would not be much time after all counselors completed training for them to complete CRAFT with CSOs.*

Data Analysis

Primary and secondary hypotheses were investigated by computing the improvement from baseline to 12-week timepoints. One-sided independent samples T-tests were used for pairwise comparisons of the three conditions. One-sided tests are appropriate for our hypothesized conditions: the alternative hypotheses for which we seek evidence is TMC is better than T, TM is better than T, and TMC is better than TM.

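### The 12-week item, as described, counts treatment entries only among CSOs the counselor says received CRAFT, so the count can differ between arms with no true difference in entry

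*Protocol*

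**What the plan says.** Protocol section 4.2 (Aim 2, data collected directly from participants) describes three linked counts, asked once: "Finally, at the 12-week follow-up only, participants will be asked to report". The first is to "report the number of CSOs they have worked with over the past 10 weeks". The next two are "how many of them they implemented CRAFT with, and how many of those CSOs had a loved one who entered new treatment". The same section rules out clinic records and CSOs as sources, so the counselor's answer is the only record of entry.

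The outcome these counts serve is wider. Protocol section 1.3 lists the counselor's report, passed on by CSOs, of identified persons (IPs) entering treatment. Hypothesis 2.5 in section 1.2 reads "Participants assigned to the TMC condition will report that more IPs have entered treatment compared to TM and T at 12-weeks", and the SAP keeps it: "2.3. Participants assigned to the TMC condition will report that more IPs have entered treatment compared to TM and T". None of these is limited to CRAFT cases. Both documents call the hypothesis exploratory because follow-up is short.

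Neither document says when CRAFT counts as implemented with a CSO, or whether the analysis variable is a count, a share of CRAFT CSOs or a share of all CSOs.

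The arms differ in how far they push counselors to use CRAFT with clients. Under section 4.1, only TMC counselors must send in recordings of client sessions, with written feedback and weekly coaching. T and TM receive weekly emails about their study materials. Under section 9.3, for TMC counselors who have trouble finding CSOs, "we will help facilitate a client match for them from our We The Village community of family members".

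**The concern.** The three counts are nested. An IP who enters treatment after the counselor worked with the CSO, but without the counselor calling that work CRAFT, falls outside the last count. Whether the label is applied is decided after randomisation by the counselor, whose training is the thing being compared. The number of recorded entries therefore mixes two quantities: how many loved ones entered treatment, and how readily counselors in that arm say they used CRAFT.

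The hypothesis concerns only the first. At stake is the reading of hypothesis 2.5 (SAP 2.3): a higher count in one arm could reflect labelling alone. Changing the denominator afterwards does not repair this, because entries outside the filter are not collected and there is no second source.

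**Working it through.** **No figure to reproduce.** The documents give no alpha, caseload, entry rate, CRAFT-use rate or power for this outcome. All values of m, p and q below are assumptions.

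**Inputs from the documents.** Arm sizes are T 15 and TMC 16 (SAP, opening section). The test is a one-sided two-sample t-test (SAP, Data Analysis). One-sided 0.05 is assumed. The item has no baseline value, so the SAP's change from baseline cannot be formed for it; the week-12 count is used.

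**Step 1: expected recorded entries.** Let m be CSOs per counselor, p the true entry rate (equal in all arms) and q the share of CSOs for whom CRAFT is reported. If labelling is unrelated to entry:

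recorded entries per counselor = m × p × q

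With equal m and p, the TMC-to-T ratio is q_TMC / q_T, whatever the entry rate.

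- m = 3, p = 0.3, q = 0.9 (TMC) v 0.4 (T): 3 × 0.3 × 0.9 = 0.81 v 3 × 0.3 × 0.4 = 0.36. Over all CSOs: 0.81/3 = 27% v 0.36/3 = 12%.
- m = 3, p = 0.3, q = 0.8 v 0.6: 0.72 v 0.54, or 24% v 18% of all CSOs.
- If TMC counselors applied the label more strictly, at 0.6 against 0.8 in T, the same sum gives 0.54 v 0.72 in favour of T.

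Dividing the filtered count by all CSOs keeps the distortion.

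**Step 2: how often the test would favour TMC with no true effect.** Simulation of 20,000 trials per row and column: Poisson caseloads with mean m, binomial entries, binomial filter, T 15 v TMC 16.

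| m | p | q: T 50%, TMC 50% | T 50%, TMC 70% | T 40%, TMC 80% | T 20%, TMC 90% |
|---|---|---|---|---|---|
| 3 | 0.2 | 5.1% | 12.6% | 27.9% | 66.3% |
| 3 | 0.4 | 5.0% | 18.6% | 46.6% | 90.6% |
| 5 | 0.2 | 4.7% | 16.5% | 40.1% | 85.2% |
| 5 | 0.4 | 5.0% | 25.5% | 63.8% | 98.5% |
| 10 | 0.2 | 5.1% | 25.4% | 63.2% | 98.5% |
| 10 | 0.4 | 4.7% | 39.9% | 88.9% | 100.0% |

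With equal shares the test behaves as it should. Counting entries among all CSOs, in the same simulated trials, gives 4.7% to 5.2% in every scenario.

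**Step 3: entries per CRAFT case.** Let qE and qN be the shares labelled CRAFT among families whose loved one did and did not enter. The recorded rate is p·qE / [p·qE + (1 − p)·qN]. At p = 0.30:

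- Labelling unrelated to entry (qE = qN): 0.30, no bias.
- qE = 0.60, qN = 0.30: 0.18 / (0.18 + 0.21) = 0.46.
- qE = 0.85, qN = 0.78: 0.255 / (0.255 + 0.546) = 0.32.

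If the second case were T and the third TMC, the rate would favour T (0.46 v 0.32), while recorded entries per CSO worked with would favour TMC (0.18 v 0.255). True entry is 0.30 in both.

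**Step 4: why the corrected item still needs a denominator.** Suppose matching gives TMC a mean of 6 CSOs against 5, with p = 0.3 in both arms. All entries are 6 × 0.3 = 1.80 v 5 × 0.3 = 1.50, and the raw all-CSO count favours TMC in about 15% of trials. Per CSO, 1.80/6 = 1.50/5 = 0.30.

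**The case against.** **The wording may cover all CSOs.** The survey form is not in the documents, and the phrase about those CSOs could point back to everyone worked with, which would fit the outcome in section 1.3. Table 3 names the measure as entry and retention, yet section 4.2 describes no retention question, so the description may be incomplete. This reading is possible but strained, because each count is introduced as a part of the one before. If the form does ask about all CSOs, the point falls.

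**More CRAFT use is part of the training effect.** It is, if it produces more entries overall, and an all-CSO count would show that. The nested item also credits an arm when total entries are identical and only the labelling differs.

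**The hypothesis is exploratory.** This stands and limits the importance of the point. But the stated reason is short follow-up, and longer follow-up would not remove the filter.

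**The direction is not shown.** A reader might infer that the item is biased toward TMC. The documents give no CRAFT-use figures, and counselors coached toward certification criteria could apply the label more strictly than those with the tutorial alone. This objection stands.

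**Two further inferences are not supported.** Because "we will recruit through free tutorials offered to OUD treatment clinics targeting those focused on family services", a reader might infer that loved ones already in treatment inflate the result. The item asks about new treatment, which partly deals with this, and recruitment precedes randomisation and applies to every arm. A reader might also want sponsor-matched CSOs removed from TMC. Matching is a conditional offer that affects caseload, not the filter, and dropping those CSOs would be a post-randomisation exclusion in one arm only.

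**Conclusion.** The concern holds in limited form. As described, the item measures something narrower than the stated outcome, and the restriction depends on a self-declared, undefined condition that assigned training can change. The between-arm count can therefore differ with no true difference in entry.

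If caseloads and entry rates are equal and labelling is unrelated to entry, the distortion of the count is exactly the ratio of CRAFT-reported shares. For CRAFT-reported shares of 50% in T and 70% in TMC, the assumed test would favour TMC in 13% to 40% of null trials over the caseloads and entry rates tried; for 40% and 80%, in 28% to 89%.

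The count would favour TMC if its counselors report CRAFT use with a larger share of their CSOs. The TMC-only recordings and coaching make that plausible, but it is an inference. The direction applies to the count, or the count over all CSOs; entries per CRAFT case could err either way. The outcome is secondary and exploratory, and nothing here touches the primary fidelity result.

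**What to change.** Reword the 12-week item:

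1. How many CSOs did you work with in the past 10 weeks?
2. Of all of these, how many had a loved one who entered new treatment, whether or not you used CRAFT?
3. Separately, with how many did you use CRAFT? Treat this as a measure of uptake.

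Add to the SAP that question 2 divided by question 1 is compared by randomised arm. Note there that caseload may itself be affected by training and by the TMC-only client matching, so the per-CSO comparison is not fully protected by randomisation. Report the number of sponsor-matched CSOs descriptively, without excluding them.

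The cost is a few reworded questions and a short SAP statement. The small downside is that counselors must recall outcomes for more clients.

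The SAP gives final enrollment and describes the analysis in the past tense, so the survey may already have been used. If it was used in the nested form, label the result as entries among self-declared CRAFT cases and draw no between-arm conclusion about treatment entry from it. The note to Table 3 plans a Phase 2 with the same assessment points, so the rewording would still be useful there.

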#### ***Data collected from other sources (identify each source; e.g., health care provider, parent, public records):***

N/A. We will only collect information directly from the study participants. We will not collect information from clinic records or directly from CSOs who participate in audio taping.

#### **4.3 Describe pre-defined criteria for removing participants from the study and the procedures for informing participants of their removal from the study. Include information on the handling of their data and measures to ensure individuals' safety and privacy after ceasing research activities.**

We do not anticipate removing participants from the study, but participants may be removed if:

- a) they break the confidentiality of other participants in the focus group (Aim 1) or clients in audiotapes (Aim 2)
- b) it becomes clear after enrollment that they do not meet the inclusion/exclusion criteria.

Participants will be notified of their removal from the study by the Principal Investigator, [name]. The PI will call the participant to explain the reason for their removal. In addition, a formal letter will be sent to participants via email. Both the phone call and letter will explain the reason for their removal, how their data will be handled, and provide referrals for support, if needed.

If any participants are removed due to breaking confidentiality during the 10-week post tutorial period when client audio tapes are submitted, we would use the data they had provided up to that point. Any participants who are removed because it is discovered that they do not meet the inclusion/exclusion criteria will have their data deleted and will not be included for analysis. All contact information will be deleted within two weeks after informing the participant of their removal. We will track and document all reasons for removing participants in order to ensure they are not rescreened and re-enrolled into the study.

